4.7.12 Spontaneous Arrhythmic Episodes

All available spontaneous arrhythmic diagnostic episodes detected by the ICD, as well as the corresponding stored IEGMs, will be retrieved via device interrogation and will be reviewed to evaluate appropriate and inappropriate ICD therapies.

4.7.13 Hospitalizations

Cardiac-related hospitalizations, emergency room visits and surgeries will be summarized using the Kaplan-Meier survival method.

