3.0 INVESTIGATIONAL PLAN

3.1 Study Design and Patient Follow-up

This is a prospective, non-randomized, multicenter, pivotal IDE study evaluating the Investigational Devices with the ST Monitoring Feature. The Analyze ST study is designed to demonstrate the safety and efficacy of the ST Monitoring Feature in the Investigational Devices. The sensitivity of the ST Monitoring Feature for detecting acute coronary syndrome events will be the primary efficacy endpoint. The primary safety endpoint will be assessed by reporting the percentage of patients who experience a false positive detection during the 12 months following a 3 month run-in period.

The goal of the 3 month run-in period is to:

1. Identify patients whose EGM rhythm or morphology is unsuitable for chronic ST monitoring
2. Provide data collection for review in order to adjust or optimize ST feature parameters

[figure not shown]
Data collection for the purposes of the FDA market approval application will be considered to be complete when the primary safety endpoint data are available and at least 41 clinical events have occurred. It is estimated that up to 5,228 patients at

Statistical Analysis Plan

approximately 200 centers will be enrolled in the study with a follow up of 12 months to meet the primary study endpoints.

A flow diagram of the study design is below.

Study Flow Diagram

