3.3.2 Exclusion Criteria

Patients will be excluded if they meet **any** of the following:

1. Are pacemaker dependent (defined as a need for ventricular pacing $\geq 20\%$ of the time)
2. Have NYHA Class IV Heart Failure
3. Have persistent or permanent atrial fibrillation
4. Have a known history of intermittent Bundle Branch Block
5. Pregnant or planning a pregnancy during the study participation
6. Have a life expectancy of < 1 year due to any condition
7. Are currently participating in a clinical investigation that includes an active treatment arm

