4.3 Analysis of Safety

4.3.1 Preliminary Safety Assessment Phase

An initial assessment of the proportion of patients free from complications due to unnecessary procedures resulting from false positive events will be conducted on the first 500 patients to complete 6 months of follow-up. In patients with an upgraded Fortify[®] ST device, the 6 months of follow-up begins with either their Baseline visit or the Baseline Upgrade visit (during which the firmware upgrade occurs). In patients with Fortify Assura ST[®] and Ellipse ST[®], the 6 months of follow-up begins with the Baseline visit. For those patients with Fortify Assura ST[®] and Ellipse ST[®], the survival time for patients who experience a complication will be calculated as the number of days from the Baseline visit (when the Patient Notifier is activated) to the date of the procedure-related complication. For those patients with Fortify[®] ST devices, the survival time will be calculated as the number of days from either the Baseline visit or the Baseline Upgrade visit (i.e., whichever visit the patient received the firmware upgrade) to the date of the procedure-related complication is first discovered. For patients who withdraw without experiencing a complication prior to analysis, their survival time will be censored at the date of withdrawal. For patients who have not experienced complications at the time of analysis, their survival time will be censored on the date of the analysis.

All patients who have the Patient Notifier turned ON at the Baseline visit or the Baseline Upgrade visit and have completed their 6-month follow up visit or 6 months of follow up since being upgraded will be included in this analysis.

Statistical Analysis Plan

Complications related to unnecessary procedures resulting from false positive events are defined as any procedure-related or test-related complications that occur in a patient in which a Type I ST episode is classified as a false positive according to the criteria described in section 3.2.3. All clinical events will be adjudicated by an independent and blinded Clinical Event Committee for the purposes of determining whether the event was related to ischemia or acute coronary syndrome and whether it was procedure or test related. Complications related to procedures or tests may include, but are not limited to:

- Air embolism
- Allergic reaction to contrast media
- AV fistula
- Bleeding
- Cardiac tamponade
- Contrast nephropathy

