4.5 Overall sample size and data cut-off

[figure not shown]
The total number of patients required for enrollment in order to satisfy the primary endpoints and the secondary endpoint is driven by the sample size requirement to satisfy the primary efficacy endpoint. Thus the total sample size required for this study is 5,228.

Data collection for the purposes of the FDA market approval application will be considered to be complete when the primary safety endpoint data are available and at least 41 clinical events have occurred.

Following submission of the clinical data, patients will continue to be followed until closure of the study for providing long-term follow up on the Investigational Devices.

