4.7.11 Clinical Events

Clinical events will be summarized for all patients in terms of the number of events and number of patients. The rate of clinical events will be reported per patient-year of follow-up along with a 95% confidence interval using Ulm's method.

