4.7.14 Mortality

The number of deaths will be summarized. The observed mortality rate will be summarized using the Kaplan-Meier survival method.

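### Section 4.7.13 summarizes cardiac hospitalizations, emergency visits and surgeries by Kaplan-Meier alone and does not say how death or repeat events are handled

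*Protocol*

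**What the plan says.** The whole of section 4.7.13, in both the Protocol and the SAP, reads "Cardiac-related hospitalizations, emergency room visits and surgeries will be summarized using the Kaplan-Meier survival method". It gives no time origin, censoring rule, treatment of death, definition of which event counts, event count or rate.

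Death is handled on its own in section 4.7.14: deaths are counted, and "The observed mortality rate will be summarized using the Kaplan-Meier survival method". Neither section refers to the other.

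The only Kaplan-Meier censoring rules written out belong to another analysis, the preliminary safety assessment in section 4.3.1. There, "For patients who withdraw without experiencing a complication prior to analysis, their survival time will be censored at the date of withdrawal", and patients without a complication are censored at the analysis date. Death is not mentioned.

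Clinical events are treated more fully in section 4.7.11: "Clinical events will be summarized for all patients in terms of the number of events and number of patients", and "The rate of clinical events will be reported per patient-year of follow-up along with a 95% confidence interval using Ulm's method".

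On follow-up, section 3.1 of the Protocol says "approximately 200 centers will be enrolled in the study with a follow up of 12 months to meet the primary study endpoints". Section 4.5 of the Protocol adds that, after the marketing submission, "patients will continue to be followed until closure of the study for providing long-term follow up on the Investigational Devices". No length is given for that later period.

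**The concern.** Two properties of the method matter here.

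First, a patient who dies can no longer be hospitalized. If that patient is censored at death, Kaplan-Meier treats the patient as still able to have the event later. One minus the curve then estimates the probability of hospitalization in a population where nobody dies, which is higher than the proportion of enrolled patients who are hospitalized. The gap widens with follow-up. If death is instead counted as an event, the curve describes hospitalization or death combined, which is also not the quantity named in the section.

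Second, a standard Kaplan-Meier curve ends for each patient at the first event. Hospitalizations, emergency visits and surgeries can recur, and no final-analysis count or rate of them is planned elsewhere.

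At stake is the accuracy and completeness of a descriptive table on use of cardiac care. No test or success criterion depends on it.

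**Working it through.** **No plan figure to reproduce.** The documents give no hospitalization rate, mortality rate, target or precision for this summary. All rates below are assumptions. The one constraint in the text is on eligibility: section 3.3.2 excludes patients who "Have a life expectancy of < 1 year due to any condition" and those in NYHA Class IV. That argues for including low mortality values in the range.

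**Inputs (assumed)**
- Annual probability of a first cardiac hospitalization, deaths aside: 30%, so h = −ln(1 − 0.30) = 0.3567 per year.
- Annual mortality among patients not yet hospitalized: 2%, 5%, 8% or 10%, so d = −ln(1 − mortality) = 0.0202, 0.0513, 0.0834 or 0.1054 per year.
- Constant hazards; deaths censored in the Kaplan-Meier estimate.
- Horizons: T = 1 year, from section 3.1, and T = 3 years, an assumption about follow-up to closure.

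**Formulas**
- One minus Kaplan-Meier = 1 − exp(−hT).
- Cumulative incidence with death competing = h/(h + d) × [1 − exp(−(h + d)T)].

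**One cell in full** (5% mortality, T = 1):
- Kaplan-Meier: 1 − 0.70 = 30.0%.
- Cumulative incidence: 0.3567/0.4080 × (1 − 0.70 × 0.95) = 0.8743 × 0.3350 = 29.3%.
- Gap: 0.7 points.
- If death were counted as an event, the curve would read 33.5%.

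**All cells**

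| Annual mortality | 1 year: 1 − KM | 1 year: cumulative incidence | Gap (points) | 3 years: 1 − KM | 3 years: cumulative incidence | Gap (points) |
|---|---|---|---|---|---|---|
| 2% | 30.0% | 29.7% | 0.3 | 65.7% | 64.1% | 1.6 |
| 5% | 30.0% | 29.3% | 0.7 | 65.7% | 61.7% | 4.0 |
| 8% | 30.0% | 28.9% | 1.1 | 65.7% | 59.4% | 6.3 |
| 10% | 30.0% | 28.6% | 1.4 | 65.7% | 57.9% | 7.8 |

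**Sensitivity to the hospitalization rate.** Letting it run from 10% to 40% a year, with mortality from 2% to 10%, gives gaps of 0.1 to 1.9 points at 1 year and 0.8 to 8.6 points at 3 years.

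**Simulation check.** With 400,000 simulated patients at 20% hospitalization and 5% mortality over 12 months, Kaplan-Meier gave 20.0% and the proportion actually hospitalized was 19.6%. The formulas give 20.0% and 19.5%.

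**Repeat events.** The share of events a first-event curve leaves out is 1 − P(at least one event)/mean count. This step ignores death over the 12 months.
- At a mean of r = 0.3567 events per patient-year, Poisson counts give 1 − 0.300/0.3567 = 16%.
- With negative binomial counts, P(at least one) = 1 − (1 + θr)^(−1/θ). Dispersion θ = 1 gives 1 − 0.263/0.3567 = 26%, and θ = 2 gives 1 − 0.236/0.3567 = 34%.
- For means from 0.105 to 0.511 per patient-year, the same formulas give 5% to 22% for Poisson counts and 10% to 42% for the two overdispersed cases.

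At 12 months, the omission of repeat events is therefore the larger part of the problem.

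**The case against.** **The text is silent; it does not lay down a wrong rule.** A reader might infer that the plan requires deaths to be censored and later events to be dropped, and hence that the bias is established. The documents do not go that far. Section 4.7.13 names a method and nothing more. Censoring at death is the usual convention, and restriction to the first event is how the standard curve works; neither is written down. This objection stands and limits the claim. It does not remove it, because counting deaths as events would not give the probability of hospitalization either.

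**The effect is small at the only horizon the plan fixes.** This stands. The 3-year figures need a follow-up length that section 4.5 does not give, and no 3-year hospitalization estimate is promised. The relevant mortality is also death before a first event, so if most deaths follow a hospitalization the gap is smaller.

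**The section does not measure the burden of false alarms.** A reader might infer that the plan's assessment of care triggered by false alarms is biased. Section 4.7.13 covers all cardiac-related care and does not isolate care prompted by an alert. False alarms and their consequences are examined elsewhere:
- board review of procedures and hospitalizations resulting from false positives (4.2);
- a table of medical care by event class in the preliminary assessment (4.3.1);
- a false positive rate using all events (4.3.3);
- procedures classified by whether they would have been done with and without the ST data (4.7.3).

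This objection stands. None of these items, nor the adverse event counts in 4.7.10, supplies a final-analysis count or rate of hospitalizations.

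**Nothing depends on the result.** The analysis is descriptive and non-comparative, with no hypothesis or threshold, and deaths are reported alongside it. This stands and sets the priority.

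**Conclusion.** The point holds as a minor one. Kaplan-Meier is the only planned summary of cardiac hospitalizations, emergency visits and surgeries, and the treatment of death and repeat events is unspecified.

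Under the usual convention, the figure reported would exceed the proportion of patients with an event. The excess is about 0.3 to 1.4 points at 12 months, and about 1.6 to 8 points if follow-up reaches 3 years. These sizes rest on assumed constant hazards, 30% annual first hospitalization and 2% to 10% annual mortality; none of these comes from the documents. The direction follows from censoring at death, which is inferred.

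The missing count and rate can be read directly from the text. The share of events that a first-event curve would omit depends on assumed event rates and dispersion.

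No primary or secondary endpoint is affected.

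**What to change.** In section 4.7.13 of both documents:

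1. Replace 1 minus Kaplan-Meier with the Aalen-Johansen cumulative incidence of the first event, with death as a competing event. State the time origin and that withdrawals are censored at withdrawal.
2. Add the number of events, the number of patients with an event and the rate per patient-year, as section 4.7.11 already does for clinical events.
3. Give the rate a patient-level bootstrap interval, because events repeat within patients. Section 4.3.3 already uses this device for the false positive rate.

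Leave section 4.7.14 as it is: Kaplan-Meier suits all-cause mortality.

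The cost is a few sentences in the SAP and a little more analysis work in standard software. Section 4.7 already lists hospitalizations and deaths among the data collected, and follow-up time is already needed for the patient-year rates, so no new data are required.

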4.7.14 Mortality

The number of deaths will be summarized. The observed mortality rate will be summarized using the Kaplan-Meier survival method.

1.0 INTRODUCTION

This document contains the statistical analysis plan for the Analyze ST IDE study using St. Jude Medical ICD systems. The Analyze ST study will include the following device models:

- Fortify[®] ST family of devices
- Fortify Assura[®] St family of devices
- Ellipse[®] family of devices

These devices will be collectively referred to as the Investigational Devices except where otherwise specified. All analyses will be carried out on the study endpoints as well as on additional data specified in this document.

2.0 PURPOSE

The intent of this study is to demonstrate the safety and effectiveness of the diagnostic ST Monitoring Feature in the Investigational Devices. Effectiveness of the device will be evaluated by analyzing the sensitivity of the ST Monitoring Feature to detect clinical events. In addition, safety of the ST Monitoring Feature will be evaluated by demonstrating a low percentage of patients with false positive events.

3.0 INVESTIGATIONAL PLAN

3.1 Study Design and Patient Follow-up

This is a prospective, non-randomized, multicenter, pivotal IDE study evaluating the Investigational Devices with the ST Monitoring Feature. The Analyze ST study is designed to demonstrate the safety and efficacy of the ST Monitoring Feature in the Investigational Devices. The sensitivity of the ST Monitoring Feature for detecting acute coronary syndrome events will be the primary efficacy endpoint. The primary safety endpoint will be assessed by reporting the percentage of patients who experience a false positive detection during the 12 months following a 3 month run-in period.

The goal of the 3 month run-in period is to:

1. Identify patients whose EGM rhythm or morphology is unsuitable for chronic ST monitoring
2. Provide data collection for review in order to adjust or optimize ST feature parameters

[figure not shown]
Data collection for the purposes of the FDA market approval application will be considered to be complete when the primary safety endpoint data are available and at least 41 clinical events have occurred. It is estimated that up to 5,228 patients at

Statistical Analysis Plan

approximately 200 centers will be enrolled in the study with a follow up of 12 months to meet the primary study endpoints.

A flow diagram of the study design is below.

Study Flow Diagram

3.2 Clinical Event Description and CEC Adjudication

Three types of events are defined in the sections below. All clinical events will be adjudicated by a Clinical Events Committee (CEC) consisting of a blinded panel of independent experts. Once the CEC adjudicates the Clinical Events, and per defined criteria in section 3.2.2, all Type I ST episodes will be classified as either False Positive or True Positive events. In addition, any Clinical Event that was not associated with a Type I ST episode detection will be classified as either False Negative or True Negative.

3.2.1 Clinical Event Committee

The CEC will include at a minimum, 2 interventional cardiologists and 2 electrophysiologists. Physicians on the CEC will not participate in the study as investigators and when reviewing events will be blinded to any patient or site information. The purpose of the CEC is to adjudicate all clinical events. Specifically:

- Classify clinical events as either an Acute Coronary Syndrome (ACS) Event, a Precursor Event, or a Non Event. Non Events will be further classified as either a Transient Ischemic Event or a Non Ischemic Event. Review all deaths, and adverse events associated with diagnostic testing or procedures performed as a result of a Type I ST Episode Detection and determine relationship to system and/or procedure.
- Review all baseline surface ECGs to determine the presence or absence of any conduction abnormality.
- Review all complications and all cardiovascular related adverse events

3.2.2 Clinical Events

ACS Events

An ACS event is defined as any of the following:

- Death due to a myocardial infarction
- A new Q-wave myocardial infarction on 12-lead ECG
- ST elevation myocardial infarction
- Biomarker evidence of acute myocardial damage*
- Evidence of new plaque rupture by invasive testing (i.e., IVUS) as adjudicated by the blinded Clinical Events Committee
- The presence of TIMI myocardial perfusion grade 0 or 1 consistent with acute injury of the myocardium from embolization
- New surface ECG ST depression or elevation treated with thrombolytic medication

Statistical Analysis Plan

- New surface ECG ST depression or elevation with new or progressive flow-limiting ischemia proven by non-invasive or invasive testing.
- Angiographic stenosis $\geq 70\%$ adjudicated by the blinded Clinical Events Committee as flow-limiting.
- An event that leads to a clinically warranted percutaneous coronary intervention (PCI) or revascularization as determined by the blinded Clinical Events Committee. Clinically warranted is defined as:
 - Angiographically visualized stenosis $\geq 70\%$ correlating with the vascular distribution in which a 12-lead surface ECG documents changes consistent with ischemia or injury in 2 or more contiguous leads
 - Angiographically visualized stenosis $\geq 70\%$ correlating with a vascular distribution shown to have ongoing ischemia by non-invasive stress testing
 - New or progressive angiographically visualized stenosis $\geq 70\%$ correlated with new or progressive anginal symptoms

*NOTE: It is recommended that the “Universal Definition of Myocardial Infarction” proposed by the Joint ESC/ACCF/AHA/WHF in 2007 be used to determine myocardial damage.

Precursor Events

A precursor event is defined as clinical symptoms of an impending ACS event followed by an ACS event within 10 days. Precursor events alone do not meet the ACS event criteria. Multiple precursor events may precede a single ACS. All precursor events will be adjudicated by the Clinical Event Committee (CEC). Symptoms identified as precursors will be grouped with the subsequent ACS event and counted as a single event. Individual precursor events will not be included in the statistical endpoint analysis.

Non Events

Non Events are defined as any clinical event that does not meet the criteria of an ACS Event or a Precursor Event. These events will be adjudicated by the CEC and will be further classified as either Transient Ischemic Events or as Non Ischemic Events.

3.2.3 Classification of Events

True Positive (TP): A Type I ST episode detection that occurs up to 72 hours prior to an ACS Event.

False Positive (FP): A Type I ST episode detection that occurs more than 72 hours prior to an ACS Event or that occurs in the absence of a true ACS Event.

True Negative (TN): Absence of a Type I ST episode detection during a Non Event.

False Negative (FN): Absence of a Type I ST episode detection within 72 hours prior to an ACS Event.

3.3 Patient Selection

3.3.1 Inclusion Criteria

Eligible patients will meet **all** of the following:

1. Have an indication for an ICD implantation or pulse generator change
2. Have documented coronary artery disease. Documented coronary artery disease is defined as having at least one of the following present a) evidence of a prior MI on ECG and/or cardiac enzymes, b) prior revascularization (by coronary artery bypass grafting or percutaneous coronary intervention) c) angina and/or ST-T wave abnormalities indicative of ischemia on exercise stress test, nuclear stress test, or echo stress test, or d) coronary artery disease diagnosed by coronary angiography.
3. Willing and able to comply with protocol requirements, including keeping all required visits
4. Willing to participate in the study and able to sign an IRB approved informed consent form
5. Willing and capable of using Merlin@home.
6. Be at least 18 years of age when enrolled in the study

3.3.2 Exclusion Criteria

Patients will be excluded if they meet **any** of the following:

1. Are pacemaker dependent (defined as a need for ventricular pacing $\geq 20\%$ of the time)
2. Have NYHA Class IV Heart Failure
3. Have persistent or permanent atrial fibrillation
4. Have a known history of intermittent Bundle Branch Block
5. Pregnant or planning a pregnancy during the study participation
6. Have a life expectancy of < 1 year due to any condition
7. Are currently participating in a clinical investigation that includes an active treatment arm

3.4 Device Description

The SJM ICD system is intended to provide ventricular anti-tachycardia pacing and ventricular defibrillation for automated treatment of life-threatening ventricular arrhythmias. AF Suppression™ pacing is indicated for suppression of paroxysmal or persistent atrial fibrillation in patients with the above ICD indication and sinus node dysfunction. In addition, the Investigational Devices have an ST Monitoring Feature that has the ability to detect ST shifts, and to record and store the associated high fidelity IEGMs during those shifts. Refer to the User's Manual for more details.

The pulse generator, along with compatible leads, constitutes the implantable portion of the ICD system.

